# 9.4.3 Safety Analyses

All safety analyses will be based on the safety population. Summary of all safety endpoints will be presented.

## 9.4.3.1 Extent of Exposure

The duration of exposure and the number of subjects exposed to study drug will be summarized by visit. The number of subjects exposed will be presented by study periods (treatment period and follow-up period).

#### 9.4.3.2 Adverse Events

Treatment-emergent adverse events (TEAEs), defined as those AEs occurring after the first administration of study treatment until the last study visit, will be tabulated in frequency tables by System Organ Class and Preferred Term based on the Medical Dictionary for Regulatory Activities (MedDRA) for each study phase. Additional summary tables will be provided for SAEs, AEs related to the study drug and/or study procedure, AESIs, and AEs leading to treatment discontinuation and study withdrawal. For a given AE, a subject will be counted once even if he/she has experienced multiple episodes of that particular AE.

Pre-treatment AEs will be listed separately.

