#### Notes:

- a Subjects are required to fast for at least 8 hours before the visit(s).
- b Visit 3 is a single visit occurring between Week 1 to Week 2.
- c For subjects that complete the Week 16 visit and will rollover to the nemolizumab LTE study, the Week 16 visit (Visit 7) will serve as the final study visit. See Section 7.6.1.
- A follow-up visit is required for subjects who discontinue after the Week 16 visit and will not rollover to the nemolizumab LTE study. The follow-up visit should occur 12 weeks after the last study drug injection. See Section 7.6.1.
- e Assessments to be conducted at the unscheduled visit(s) depend on the reason for the visit. See Section 7.6.2.
- Subjects who discontinue before the Week 16 visit should attend an early termination visit and a follow-up/final study visit 12 weeks after the last study drug injection. See Section 7.6.1.

CONFIDENTIAL Page 37 of 99

Galderma Research & Development, LLC Protocol Number: RD.06.SPR.116912 21-JUL-2020 Version 6.0

- g Patient-reported efficacy measurements (ACT and DLQI/cDLQI) should occur before investigator (efficacy and safety) assessments, blood sample collections, and study drug administration.
- h Peak and average pruritus NRS should be recorded by subjects once daily in the evening, beginning ≥ 2 weeks before Day 1.
- Sleep disturbance NRS should be recorded by subjects once daily in the morning, beginning ≥ 2 weeks before Day 1.
- Subjects will be asked to record the response (yes/no) to the following question each evening, "Did you apply the eczema medication your doctor gave you, to your skin today?", beginning ≥ 2 weeks before Day 1. See Section 7.5.8.1.1.
- Subjects with a history of asthma will complete the ACT at each study visit before physical examination and other investigator assessments. Subjects with de novo diagnosed asthma will complete the ACT beginning at the first visit of de novo diagnosis and at all follow-up study visits.
- Subjects aged 17 years or older will complete the DLQI, while subjects aged 12-16 years old will complete the cDLQI.

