10.2. Adverse Events

Adverse events (AEs) will be coded using the Medical Dictionary for Regulatory Activities (MedDRA) Version 21.1. Summaries of AEs will include only treatment emergent AEs (TEAEs) defined as AEs with an onset date/time on or after the date/time of first treatment. AEs with completely missing onset dates/time will be considered as TEAEs. If AE onset date/time is partially missing, the AE will be considered as TEAE unless the non-missing part of date/time proves it started prior to the first treatment date/time.

AEs will be summarized using the number and percent of subjects reporting each system organ class (SOC) and preferred term (PT) and sorted alphabetically by SOC and by descending frequency of PT within SOC. Subjects who experienced multiple events within the same SOC will be counted once in the SOC summary. Subjects who experienced multiple occurrences of events with the same PT will be counted once in the PT summary. Percentages will be calculated using the total number of subjects in the Safety population.

The following summary tables for AEs will be presented:

- Overall Summary of Treatment Emergent Adverse Events (TEAEs), All Causalities
- Overall Summary of Treatment Emergent Adverse Events (TEAEs), Study Drug Related
- Treatment-Emergent Adverse Events (TEAEs) by System Organ Class and Preferred Term, All Causalities
- Treatment Emergent Adverse Events (TEAEs) by System Organ Class and Preferred Term,
 Study Drug Related
- Serious Treatment-Emergent Adverse Events (TEAEs) by System Organ Class and Preferred Term, All Causalities
- Serious Treatment Emergent Adverse Events (TEAEs) by System Organ Class and Preferred Term, Study Drug Related

- Treatment-Emergent Adverse Events (TEAEs) by System Organ Class, Preferred Term, and Maximum Severity, All Causalities
- Severe Treatment Emergent Adverse Events (TEAEs) by System Organ Class and Preferred Term, All Causalities
- Severe Treatment Emergent Adverse Events (TEAEs) by System Organ Class and Preferred Term, Study Drug Related
- Treatment-Emergent Adverse Events (TEAEs) Leading to Permanent Discontinuation of Study Drug by System Organ Class and Preferred Term, All Causalities
- Treatment Emergent Adverse Events (TEAEs) Leading to Permanent Discontinuation of Study Drug by System Organ Class and Preferred Term, Study Drug Related
- Treatment-Emergent Adverse Events (TEAEs) of Special Interest by System Organ Class and Preferred Term, All Causalities

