10.9. Other Safety

Confirmed pregnancy test results, childbearing potential, premense status results, biomarker and virology assessment data will be presented in a listing.

11. Immunogenicity

Blood samples will be collected to assess anti-drug (anti-nemolizumab) antibodies (ADA). Serum samples will be assessed for ADA at Baseline, Weeks 4, 8, 16, 24 and at any unscheduled visit for safety reasons.

Screening ADA, confirmation ADA, ADA titer, nutralizing antibodies, and treatment-related ADA will be will be summarized for the Safety population (scheduled visits only).

A treatment-related ADA is a post-baseline confirmatory ADA sample showing positive results while the baseline sreening or confirmatory ADA sample shows negative results.

All Immunogenicity data will be listed for the Safety population.

12. Health Economics

Not applicable.

13. Interim Analyses

An interim analysis is planned after approximately 10 subjects complete the Week 8 visit. The study will attempt to enrol at least 3 subjects with a low body weight (≤ 61 kg) for the interim analysis and approximately 6 total subjects with low body weight for the overall study population, with investigators attempting to enrol subjects at the lower age range (12-14 years old). The interim analysis will assess whether the observed safety and PK data from adolescents are similar to the data obtained in adults, which is the basis for allowing recruitment of adolescent subjects into the planned nemolizumab Phase 3 studies for AD (pivotal and open-label extension protocols).

Outputs presented for the interim analysis and for the IDMC are marked in Sections 18 (Index of Tables), Section 19 (Index of figures) and Section 20 (Index of Listings). But the selected output list for IDMC meeting can be updated by IDMC member's request.

14. Changes from Analysis Planned in Protocol

No changes to the methods planned in the protocol are foreseen.

15. Reference List

Not applicable.

16. Programming Considerations

All TLFs and statistical analyses will be generated using SAS® 9.4 or higher (SAS® Institute Inc., Cary, NC, USA). Computer-generated table, listings and figures (TLF) output will adhere to the following specifications.

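### The protocol asks for TEAE tables by study phase, but the SAP pools all follow-up, so the final TEAE percentages depend partly on how many subjects roll over at Week 16

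*Protocol*

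**What the plan says.** **What is to be tabulated.** Protocol Section 9.4.3.2 plans TEAE tables by system organ class and preferred term, "based on the Medical Dictionary for Regulatory Activities (MedDRA) for each study phase". It lists pre-treatment events separately and describes TEAEs as "defined as those AEs occurring after the first administration of study treatment until the last study visit". Study phase is not defined, but Section 9.4.3.1, just before it, presents the number of subjects exposed by two periods, treatment and follow-up.

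**What the SAP provides.** SAP Section 10.2 counts as TEAEs all "AEs with an onset date/time on or after the date/time of first treatment", with no end date and no division by period. On denominators it says: "Percentages will be calculated using the total number of subjects in the Safety population". The indexed TEAE tables, 14.3.1.1.1 to 14.3.1.2.12, are split by causality, seriousness, severity and similar features, but none by period. SAP Section 14 states: "No changes to the methods planned in the protocol are foreseen".

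**How long subjects are observed.** For subjects who complete Week 16 and enter the extension study, the notes to Protocol Section 7.2 say that "the Week 16 visit (Visit 7) will serve as the final study visit". SAP Section 3.3 schedules a Week 24 visit for those who do not roll over immediately, and follow-up for 12 weeks after the last dose for those who stop before Week 16.

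**The concern.** Incidence of TEAEs, AESIs and SAEs is a primary safety endpoint (Protocol Section 6.2.3). A crude percentage can be read only if one knows the period it covers. Here a subject's observation time depends in part on an administrative event, entry into the extension study. A pooled percentage over all Safety subjects is then neither a 16-week nor a 24-week incidence, and it does not show whether events arose during treatment or afterwards.

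The SAP already has what it needs to separate the two. Section 6.2 defines the treatment period. Section 7.6 splits rescue medication into treatment and follow-up periods, with paired tables 14.1.4.3 and 14.1.4.4. Sections 10.3 and 10.4 restrict the last post-baseline laboratory and vital-sign results to the treatment period. The TEAE tables, which the protocol asks to be split, are not.

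**Working it through.** **Step 1: the texts side by side.** The protocol asks for TEAE tables per phase. The SAP has only pooled TEAE tables and declares no change. A TEAE cannot precede the first dose, so the phases that can apply are treatment and follow-up. The mismatch is textual and needs no assumption beyond that reading.

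**Step 2: observation time, from the visit schedule in Protocol Section 7.2.**
- Rollover subject: (113 − 1)/7 = 16 weeks.
- Non-rollover subject: (169 − 1)/7 = 24 weeks, which is also the Week 12 last dose plus 12 weeks.
- Early discontinuer: last dose at Week 0, 4, 8 or 12, plus 12 weeks, gives nominally 12, 16, 20 or 24 weeks.
- For 20 completers: 20 × 16 = 320 subject-weeks if all roll over, 400 if half do, and 20 × 24 = 480 if none do.

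**Step 3: effect on the pooled percentage.** The documents give no adverse event rate and no rollover fraction, so there is no figure of the plan's own to reproduce. Assume a constant hazard, a 16-week incidence p16 and a rollover fraction r among completers:

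p24 = 1 − (1 − p16)^(24/16); pooled = r × p16 + (1 − r) × p24

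For p16 = 20%: p24 = 1 − 0.8^1.5 = 28.4%. For p16 = 50%: p24 = 1 − 0.5^1.5 = 64.6%.

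| p16 (assumed) | r = 100% | r = 75% | r = 50% | r = 25% | r = 0 |
|---|---|---|---|---|---|
| 5% | 5.0% | 5.6% | 6.2% | 6.8% | 7.4% |
| 20% | 20.0% | 22.1% | 24.2% | 26.3% | 28.4% |
| 50% | 50.0% | 53.7% | 57.3% | 61.0% | 64.6% |

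A treatment-period table has expected value p16 among completers, whatever r is.

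**Step 4: if the hazard falls off drug.** The last dose is at Week 12. If the hazard in Weeks 16 to 24 is half its previous level, the exponent becomes 1 + 0.5 × 8/16 = 1.25. Then p24 = 1 − 0.8^1.25 = 24.3%, or 1 − 0.5^1.25 = 58.0%. If no first events occur after Week 16, the shift is zero.

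**Step 5: against sampling error at n = 20.** The standard error is √(0.2 × 0.8/20) = 8.9 points at 20% and √(0.5 × 0.5/20) = 11.2 points at 50%. The largest shifts, 8.4 and 14.6 points, are about 0.9 and 1.3 standard errors. Both lie inside 1.96 standard errors (17.5 and 21.9 points).

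**The case against.** The best defence is that little turns on this. The study is small, single-arm and descriptive, with no safety hypothesis and no numerical margin. Every TEAE is listed by subject, so a reader could rebuild the split. The shift is smaller than the sampling uncertainty, and drug levels are expected to be below quantification by the end of follow-up, so a constant hazard probably overstates it. All of this stands and limits the weight of the point. It does not remove the departure from the protocol, and imprecision is no reason to report a percentage without a defined time window.

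Three narrower objections also stand in part.

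- A reader might infer that the SAP created the unequal window by leaving out an end date. It did not. The protocol's own TEAE window ends at each subject's last visit, and adverse event collection stops with the study, so the missing end date changes little in practice. The protocol also does not say that the by-phase tables were meant to deal with rollover. What the SAP lost is the one planned output that would separate the periods.
- The division into 16 and 24 weeks may not be clean. Protocol Section 8.6.1 has subjects followed for adverse events for 12 weeks after the last dose, with no exception for rollover. For a Week 12 last dose that runs to Week 24, eight weeks beyond the visit that Section 7.2 calls final for rollover subjects. Sections 8.6.1.3 and 8.6.1.4 set the same 12-week limit for SAE and AESI reporting.
- A treatment-period table is not a pure 16-week incidence. Under SAP Section 6.2 a discontinuer's treatment period ends at the earlier of early termination or 4 weeks after the last injection, so a subject dosed only on Day 1 contributes at most 4 weeks. The table removes dependence on rollover, not on early discontinuation.

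**Conclusion.** The protocol and the SAP disagree on whether TEAEs are tabulated by phase, and the SAP does not declare the difference. As a result, the final pooled crude incidence of a primary safety endpoint depends partly on the rollover fraction. The illustrated size, 20% reading as 20% to 28% and 50% as 50% to 65% over the full range of rollover, rests on an assumed constant hazard and assumed event rates. If all or none of the completers roll over, the mix among them disappears, but the mismatch between the documents remains.

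A reader might go further and infer that the planned comparison with adults is distorted. The documents do not support that. The only adult comparison they specify is the interim one, triggered when about 10 subjects have completed Week 8, before rollover matters for most subjects. Unequal observation at that point would come mainly from staggered entry. The adult observation window is not available in the documents either, so a 16-week window cannot be shown to be the matching one.

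This is a modest point, worth correcting because the correction is cheap.

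**What to change.** 1. For the final analysis, add TEAE, SAE, AESI and drug-related TEAE tables for (a) the treatment period as defined in SAP Section 6.2, with the Safety population as denominator, and (b) the follow-up period, with subjects entering follow-up as denominator, because rollover subjects are not in follow-up.
2. Keep the overall table, preferably with exposure-adjusted rates (events or first events per subject-week observed), since early discontinuers still have shorter observation in (a).
3. State in the SAP that study phase means these two periods. If the by-period tables are not wanted, record the departure in SAP Section 14.
4. Reconcile the 12-week adverse event follow-up in Protocol Section 8.6.1 with the Week 16 final visit for rollover subjects in Section 7.2, and say in which study's data any events from Week 16 to Week 24 in those subjects are counted.

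The cost is a few repeat tables built from adverse event onset dates and period definitions already in the SAP. No new data or visits are needed. The downside is that some of the added tables, follow-up above all, will have small counts.

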# 9.4.3.3 Electrocardiogram

All ECG changes from screening at Week 16 and unscheduled visits will be summarized for safety reasons.

## 9.4.3.4 Clinical Laboratory

Laboratory data (absolute values and change from baseline) will be summarized. In addition, the number and percent of subjects below, within, and above the laboratory reference ranges will be summarized by visit. Shift tables will be generated using the reference ranges.

Abnormal laboratory values from tests performed on the baseline visit will not be considered as TEAEs, because the sample collection will be conducted before study drug administration.

## 9.4.3.5 Vital Signs

All vital signs and weight data (absolute values and change from baseline) will be summarized by visit. In addition, the number and percent of subjects with clinically significant abnormal values of clinical concern will be summarized.

CONFIDENTIAL Page 75 of 99

#### 9.4.3.6 Asthma Control Test

Total ACT scores will be summarized by visit.

# 9.4.3.7 Peak Expiratory Flow

Peak expiratory flow measurements (absolute values and change from baseline) will be summarized by visit.

Further details on the safety analyses will be provided in the SAP.

## 9.4.4 Efficacy Analyses

Primary inference for all the efficacy analyses will be based on the ITT population at the Week 16 endpoint.

All efficacy variables will be summarized by visit. The categorical variables will be summarized by frequency and percentage for each response category (N, %). The continuous variables will be summarized using mean, median, minimum, maximum, and standard deviations for the data collected at each visit. Further details on efficacy analyses will be provided in the SAP.

# 9.4.5 Biomarker Analyses

Primary inference for all biomarker analyses (including eosinophil, TARC, IgE, etc) will be based on the observed cases. All biomarker variables (eg, absolute and change from baseline) will be summarized descriptively at each time point. If the variable is not Gaussian distributed then it will be log transformed. In addition, a box-plot will be produced at each time point. Biomarker analysis will be conducted by the designated CRO based on a separate biomarker analysis plan.

# 9.4.6 Quality of Life Analyses

Primary study population for all QoL analyses will be based on ITT population. The DLQI/cDLQI data will be summarized descriptively by analysis visit. Details of the analyses will be provided in the SAP.

#### 9.5 Sample Size Assumption

Based on the variability of nemolizumab serum concentrations (observed in adults during previous studies), a sample size of 20 was considered sufficient to calculate PK parameters with adequate precision and to ensure adequate representation across the adolescent age range. No formal powering of the trial was performed to determine sample size requirement.

The study will attempt to enroll at least 3 subjects with low body weight ( $\leq$  61 kg) for the interim analysis and approximately 6 total subjects with low body weight for the overall study population.

CONFIDENTIAL Page 76 of 99

## 9.6 Protocol Deviations

All protocol deviations related to study inclusion or exclusion criteria, conduct of the study, subject management, or subject assessments will be identified, evaluated, and resolved (if applicable) before the respective database lock (interim or final analysis), and will be described in the final SAP / clinical study report.

CONFIDENTIAL Page 77 of 99

# 10 Quality Assurance and Quality Control

# 10.1 Audit and Inspection

Study centers and study documentation may be subject to Quality Assurance audit during the course of the study by the sponsor or its nominated representative. In addition, inspections may be conducted by regulatory authorities at their discretion.

## 10.2 Monitoring

Data for each subject will be recorded on CRFs. Data collection must be completed for each subject who signs an informed consent form (ICF) and is administered study drug.

In accordance with current Good Clinical Practice (GCP) and ICH guidelines, the study monitor will carry out source document verification at regular intervals to ensure that the data collected in the CRF are accurate and reliable.

The investigator must permit the monitor, the IEC/IRB, the sponsor's internal auditors, and representatives from regulatory authorities direct access to all study-related documents and pertinent hospital or medical records for confirmation of data contained within the CRFs.

# 10.3 Personnel Training

Study monitors and all relevant personnel will be trained before study initiation on the condition to be treated, the Standard Operating Procedures (SOPs) to be used in this clinical trial, the protocol, and all study-specific procedures. Team organization, communication, and operational issues will also be discussed and agreed upon.

Investigators, evaluators, study coordinators, pharmacists and other applicable personnel are recommended to attend an investigator meeting. During the meeting, participants will be trained on the protocol, ICH-GCP, study-specific procedures (including efficacy assessment scales and instruction for use of the study drug), IRT and CRF completion.

All personnel involved in the study conduct will receive training before participating in any procedure and/or evaluation. Each study center will have a training record as part of the site file and Trial Master File.

## 10.4 Data Management and Coding

The designated CRO will be responsible for activities associated with the data management of this study. This will include, but is not limited to, setting up a relevant database and data transfer mechanisms, along with appropriate validation of data and resolution of queries. All data management activities will be detailed in the data management plan (DMP).

Study centers will enter data directly into an electronic data capture (EDC) system by completing the CRF via a secure internet connection. Data entered into the CRF must be verifiable against source documents at the study center. Data to be recorded directly on the CRF will be identified

CONFIDENTIAL Page 78 of 99

and the CRF will be considered the source document at the study center. Data to be recorded directly on the CRF will be identified, and the CRF will be considered the source document. Any changes to the data entered into the EDC system will be recorded in the audit trail.

#### 10.5 Clinical Trial Conduct

With the exception of avoiding an immediate risk to a subject, the investigator should not deviate from the clinical trial protocol or implement any changes without written approval from the sponsor and prior review and documented approval/favorable opinion from the IRB/IEC of a protocol amendment.

Changes that involve only logistical or administrative changes to the clinical trial protocol are authorized. The investigator should document and explain any deviation from the clinical trial protocol.

#### 10.6 Amendments

The sponsor may modify the clinical trial protocol at any time for ethical, medical, or scientific reasons. Any amendments will be handled according to applicable local regulations.

The sponsor does not have to notify non-substantial amendments to the competent authorities or IRB/IEC. However, non-substantial amendments will be recorded and detailed in subsequent submissions (eg, in the subsequent notification of a substantial amendment).

